4.4.1.3. Sensitivity Analysis

The analysis (in Section 4.4.1.2) will be repeated for mITT population, including participants inadvertent enrolled, for both treatment regimen estimand and efficacy estimand. For the time in glucose range between 70 and 180 mg/dL (3.9 and 10.0 mmol/L) inclusive measured by CGM, a sensitivity analysis will be performed on the treatment regimen estimand, using the same ANCOVA model described in Section 4.3.2 but assuming unequal variances in order to account for potential unequal residual variances due to different group sizes.

4.4.2. Supportive Secondary Endpoints

4.4.2.1. Other Efficacy Endpoints

The analysis of continuous efficacy measures of change from baseline for:

- HbA1c at Weeks 52 and 78 (Visits 30 and 37),
- fasting glucose by SMBG at Weeks 26, 52 and 78 (Visits 22, 30 and 37), and
- CGM (selected) parameters at the 4-week sessions prior to Weeks 26, 52 and 78 (Visits 22, 30 and 37)

will be based on both treatment regimen estimand and efficacy estimand. Analysis of insulin dose will be based on efficacy estimand only.

For treatment regimen estimand, only participants with an observation either at baseline or at the endpoint visit will be included in the analysis. The missing baseline will be imputed using multiple imputation under assumption of missing at random. Missing data at the endpoint visit will be imputed using either retrieved dropout or return-to-baseline multiple imputation approach determined by the criterion described for the primary efficacy endpoint in Section 4.3.2. ANCOVA analysis will be conducted similar to that for the primary endpoint. An additional term of baseline HbA1c stratum (<8.0%, $\geq 8.0\%$) will be added into the model for the endpoints except analysis of HbA1c.

For efficacy estimand, participants with baseline and at least one post baseline observation will be included in the analysis. The longitudinal observations of actual and change from baseline in HbA1c up to Week 78 will be analyzed using the same MMRM model as for the efficacy estimand described in Section 4.3.2. The analyses of other continuous efficacy measures (insulin dose, fasting glucose and CGM parameters) will use an MMRM model similar to that for the primary endpoint with an additional term of baseline HbA1c stratum (<8.0%, $\geq 8.0\%$). A compound symmetry covariance structure will be used to model the within-participant errors for fasting glucose from SMBG and insulin dose.

Additional analysis are as specified below.

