## Justification for the insulin degludec starting dose

The starting dose for insulin degludec (U100) is the same as the daily dose of basal insulin the participant was taking prior to Visit 3 (Week 0). Insulin degludec will be titrated to achieve FBG target of 80-120 mg/dL (4.4-6.6 mmol/L) using an algorithm that is patterned after the well-established Riddle algorithm and other published algorithms (Meneghini et al. 2007, Kadowaki et al. 2017) but modified to balance efficacy and hypoglycemia for the same FBG targets as LY3209590 (Section 6.1).

Safety of study participants will be closely monitored during the early stages of dose titration to determine whether adjustments to the dose are needed to safely achieve FBG targets of 80-120 mg/dL (4.4-6.6 mmol/L) and will continue throughout the study (See Section 6.1).

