## **Insulin Dose Titration and Dose Maintenance**

In this treat-to-target study, both treatment groups will undergo titration to achieve and maintain an FBG target within the range of 80-120 mg/dL (4.4-6.6 mmol/L). Active titration will occur in both treatment groups between Visits 3 to 15 (Weeks 0 to 12) which will be designated as the Titration Period with the goal to achieve insulin dose stabilization by Visit 15 (Week 12) with a minimum of monthly adjustments as necessary during the Maintenance Period from Visit 15 to 37 (Weeks 12 to 78).

Using the e-diary-linked study-provided glucometer, participants in both treatment groups will perform daily self-monitored FBGs. A minimum of 3 FBG readings on separate days each week must be obtained so that investigators can review the data to make dose adjustments using the titration algorithms for once-weekly or once-daily insulins (Sections 6.1.4 and 6.1.5). The median FBG to use in determining the dose adjustments starting at Visit 5 (Week 2) is obtained from the 3 most recent FBGs in the previous week. The median is the middle value when the 3 values are placed in ascending or descending order. For example, if a participant's FBGs for the past 3 consecutive measurements were 180, 202, and 190, the median is 190.

**Note:** If the participant has only 2 FBG readings for the week, then the lesser of the readings should be used to determine the dose adjustments. If only 1 FBG measurement is available, determination if dose is changed using only a single FBG value is at the discretion of the investigator.

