#### 6.1.5. Insulin degludec Dose Initiation and Modification

In this section, dosing instructions for insulin degludec are provided for

- dose initiation at Visit 3 (Week 0), and
- administration of the daily dose at Visit 4 (Week 1) and subsequent dosing/dose adjustments throughout the treatment period.

Note: The first dose is administered by site personnel; subsequent doses are self-administered.

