# Visit 3 – (Week 0): Randomization Visit Insulin Degludec Dose Determination from Equivalent of Prestudy Insulin Dose

Follow instructions in the Equivalent Dose of Insulin Degludec table below, to calculate the equivalent dose of insulin degludec to be administered by the participant once daily.

**Note:** If a participant is on NPH twice-daily or U300 glargine, the prestudy basal insulin dose should be reduced by 20% when determining the once-daily dose of insulin degludec to initiate in the study.

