4.4.2.1.2. Study Insulin Dose Analysis

For study insulin dose, the average daily dose in U, weekly dose in U and daily dose in U/kg during each visit for individual participants will be used in the analysis.

In the LY3209590 group,

- the average dose of each visit (that is, average of weekly doses since last visit) will be used as the average weekly dose in U;
- the average daily dose in U will be the average weekly dose in U divided by 7;
- the average daily dose in U/kg will be the average daily dose in U divided by body weight for the visit.

In the insulin degludec group,

- the average dose of each day within a visit (that is, average of each day doses since last visit) will be used as the average daily dose in U;
- the average weekly dose in U will be calculated by the average daily dose in U multiplied by 7;
- the average daily dose in U/kg will be the average daily dose in U divided by last measured body weight on or prior to the visit.

For participants using typical once-daily pre-study basal insulin, the average pre-study basal dose during the lead-in period will be the baseline daily dose in U. For participants using pre-study U-300 or NPH BID, the average pre-study basal dose during the lead-in period multiplied by 0.8 will be the baseline daily dose in U. The baseline daily dose in U multiplied by 7 will be the baseline weekly dose in U for the study insulin dose analysis. The baseline daily dose in U divided by baseline weight will be the baseline daily dose in U/kg.

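### SAP 4.4.2.1 fits insulin dose with unqualified compound symmetry, in effect one variance for 34 visits; dose CIs at Weeks 26, 52 and 78 are likely miscalibrated

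*SAP*

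**What the plan says.** SAP 4.4.2.1 analyses insulin dose with an MMRM similar to the primary one, plus a baseline HbA1c stratum term, but sets the covariance separately: "A compound symmetry covariance structure will be used to model the within-participant errors for fasting glucose from SMBG and insulin dose". It adds: "Analysis of insulin dose will be based on efficacy estimand only". The primary model in SAP 4.3.2 (and Protocol 9.3.2) starts from an unstructured covariance and falls back through six structures. Compound symmetry with heterogeneous variances is third and compound symmetry without them is sixth.

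The dose variable is defined in SAP 4.4.2.1.2. For LY3209590 the visit value is the "average of weekly doses since last visit"; for degludec it is the corresponding average of daily doses. The baseline covariate is the average lead-in dose; for U-300 or NPH BID users, "the average pre-study basal dose during the lead-in period multiplied by 0.8 will be the baseline daily dose in U".

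The dosing rules lie close to that covariate. Protocol 4.3 says: "The starting dose for insulin degludec (U100) is the same as the daily dose of basal insulin the participant was taking". Protocol 6.1.5 has the dose for twice-daily NPH or U300 glargine "reduced by 20% when determining the once-daily dose of insulin degludec to initiate in the study", which matches the SAP factor of 0.8. Section 6.1.5 then covers "administration of the daily dose at Visit 4 (Week 1) and subsequent dosing/dose adjustments throughout the treatment period". For LY3209590, Protocol 6.1.4 gives the Starting Weekly Dose (seven times the daily dose) at Visit 4, or 40 units less after qualifying hypoglycemia. Protocol 6.1.3 aims for stable doses by Week 12, with at least monthly adjustments as needed to Week 78.

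**The concern.** Homogeneous compound symmetry gives every visit the same residual variance and therefore, with complete data, the same standard error for the treatment difference. If early visits have little spread around the baseline covariate and later visits have much more, the pooled variance is too small for the later visits. Their confidence intervals are then too narrow and their p-values too small. Kenward-Roger degrees of freedom do not correct a wrong variance structure.

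Insulin dose at Weeks 26, 52 and 78 is a listed other secondary endpoint, and SAP 4.1 displays treatment differences with 95% CIs and p-values. SMBG fasting glucose, named in the same sentence, also has a treatment regimen ANCOVA; dose has no such second analysis.

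**Working it through.** The documents give no SD, power or precision for insulin dose, so there is no stated figure to reproduce. The variance paths below are assumptions.

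**Inputs.** Visits 4 to 37 in the schedule of activities give 34 post-baseline visits: 19 by Week 26, and 11 before Week 12. Allocation is 626:313 (Protocol 1.1).

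**Formula.** Let v(t) be the residual variance at visit t, the same in both arms. With complete data and treatment-by-visit terms, the compound-symmetry SE uses the mean of v over visits:

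- ratio = SE(CS) / SE(true) = sqrt(mean v / v(t))
- type I error = 2 × (1 − Φ(1.96 × ratio))

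**Loading dose excluded, spread flat from Week 12.** Let x = min((week − 1)/11, 1). Weeks 1 to 12 contribute 66/11 = 6 to the sum of x and the other 22 visits contribute 22, so mean x = 28/34 = 0.824. For x², the mean is (506/121 + 22)/34 = 0.770.

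| Path, final variance = 1 | Mean v | Ratio | Type I error |
|---|---|---|---|
| Only Week 1 low (zero) | 33/34 = 0.971 | 0.985 | 5.35% |
| 0.15 + 0.85x | 0.850 | 0.922 | 7.1% |
| x (variance linear from 0) | 0.824 | 0.907 | 7.5% |
| x² (SD linear from 0) | 0.770 | 0.878 | 8.5% |

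The 15% start allows for a common baseline slope other than 1. For example, slope 1.25, baseline SD 18 and final SD 12 give (0.25 × 18)²/12² = 14%.

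**Earlier settling.** With the linear-variance path flat from Week 4, mean v = 32/34 and type I error is 5.7%. Flat from Week 6, mean v = 31/34 and it is 6.1%.

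**Spread that keeps growing.** The ratio then differs by visit. A simulation of the dosing rules under an assumed FBG response, loading dose excluded, gave these coverages at Weeks 26, 52 and 78:

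- middle case: 93.3%, 90.5%, 88.9%
- quick stabilization: 94.0%, 92.7%, 91.9%
- strong growth: 93.6%, 86.2%, 82.5%
- almost no dose change: 95.0%, 94.9%, 94.7%

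Visit-specific variances brought the middle case to about 95.2% to 95.5%.

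**Model-fit check.** The compound-symmetry model was fitted by REML to 1,000 simulated trials per setting (Monte Carlo error about 0.8 points), with true correlation 0.7, at Week 78. A flat-variance control gave 5.3%. The last three paths in the table gave 7.0%, 7.2% and 8.6%. With dropout of 15% at Week 26 (the plan's figure) and 25% at Week 78 (assumed), the control gave 5.2% and the paths 8.2%, 8.7% and 10.0%. Sandwich standard errors gave 5.2% to 5.8%.

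**Loading dose counted.** Take everyone at the protocol's example of 30 units/day. If only the Visit 3 dose enters the first average, a loaded participant has 630/7 = 90 units/day and an unloaded one 210/7 = 30. With a proportion p loaded, Week 1 LY3209590 variance is 60² × p(1 − p). For p = 0.7 this is 756, and weighting the arms 2:1 (degludec at 0) gives 504. With final SD 12 and the linear-variance path:

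- mean v = (28 × 144 + 504)/34 = 133.4
- ratio = sqrt(133.4/144) = 0.963, type I error 5.9%

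Over p = 0.5 to 0.9, final SD 8 to 16 and the last three paths in the table, the ratio runs from 0.89 to 1.06 and type I error from 8.1% down to 3.8%.

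The result depends on the interval rule. If the Visit 4 dose is averaged in, the loaded value is (630 + 210)/2/7 = 60. The pooled Week 1 variance becomes 30² × 0.21 × 2/3 = 126, and type I error is 7.1%. If the loading dose falls in a separate Week 0 row (35 visits), mean v = (4,032 + 504)/35 = 129.6 and type I error is 6.3%.

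**The case against.** The strongest reply is that no document gives dose variances, so neither the size nor, in every case, the direction of the error is established. That stands. A reader might infer from the first table that coverage is about 91.5% to 93% at all three endpoint visits. The documents do not support that: equal ratios across visits follow only from the assumed flat spread after Week 12, which the protocol states as a goal while adjustments continue to Week 78.

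A reader might also infer that the first degludec average equals the baseline covariate exactly. It does not. The starting dose uses the usual lead-in dose, while the SAP covariate is the average one. Investigators may depart from the algorithm, and SAP Appendix 2 plans to count such departures. The U/kg outcome divides by on-study weight. Protocol 6.1.5 lists what it covers from Visit 4 and does not expressly forbid an earlier change. What remains is low spread at the first visit, which is enough for the argument.

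The loading dose can fairly be read as excluded, because Protocol 6.1.2 gives loading and weekly doses separate maxima. Applied to dose, the SAP 4.1 interval rule for SMBG (after the prior visit, up to the visit day) would place it at Week 0. These are readings; the SAP states no rule for dose.

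A parsimonious structure is also reasonable with 34 visits, since unstructured needs 34 × 35/2 = 595 parameters. That justifies avoiding unstructured, but not forcing equal variances. Finally, the heterogeneous form may have been meant; the text does not say so.

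**Conclusion.** The point holds as a minor correction. The wording most naturally gives one residual variance across 34 dose visits, and the dosing rules make a constant variance implausible. The 95% CIs and p-values for dose at Weeks 26, 52 and 78 are therefore likely miscalibrated.

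With the loading dose excluded, complete data and spread flat after Week 12, type I error is about 5.4% to 8.5%. This rests on assumed variance paths. Earlier settling moves it towards 5%, continued growth makes Weeks 52 and 78 worse, and a counted loading dose can take it below 5%. If doses barely change and the loading dose is excluded, the effect is close to nil.

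Insulin dose is outside multiplicity control (SAP 2.1), and the primary and key secondary tests are unaffected. The planned visit SDs would reveal unequal spread but not correct the intervals. Because SMBG fasting glucose shares the sentence, a reader might extend the point to it. The argument depends on how doses are started and titrated and gives no ground for changing that model.

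**What to change.** For insulin dose only, replace the single structure with the heterogeneous-variance members of the Section 4.3.2 list, in order: Toeplitz, autoregressive, then compound symmetry. With 34 visits these need 67 (34 variances + 33 correlations), 35 and 35 parameters. If only a homogeneous structure converges, report empirical (sandwich) standard errors and name the degrees-of-freedom method used with them, since the plan otherwise specifies Kenward-Roger. If heterogeneous compound symmetry was already meant, say so.

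Also state:

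- whether the one-time loading dose enters the first post-baseline dose average in the model;
- which dates bound each visit's dose interval;
- whether Week 0 is a model visit.

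The cost is a few sentences of SAP text before database lock and some extra computing, with possible convergence steps in the 34-visit model.

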4.4.2.1.1. Analysis for CGM Parameters

The time in glucose ranges will be based on the percentage and time of CGM readings within the glucose ranges, and glucose variability will be based on the readings during the specific CGM session. Section 6.6 (Appendix 6) provides the derivation of CGM parameters .

Longitudinal logistic regression model with independent variables of treatment, strata (country, the type of basal insulin at randomization, and, baseline HbA1c stratum), visit and treatment-byvisit interaction and baseline of the dependent variable will be used to analyze CGM targets of glycemic controls (see Section 6.6.1). Same order of variance-covariance structures will be used as mentioned for MMRM in Section 4.3.2 for selection.

The time point for primary CGM data analysis is CGM session. In addition, the average time in glucose range, hypoglycemia range and hyperglycemia range by week (by visit for treatment period) will be summarized by treatment. Average daily time since last dose by CGM Session during treatment period will also be summarized for LY3209590.

Missing data patterns will be summarized at daily, weekly (visit) and CGM session levels.

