4	prior to the database lock	Added sensitivity analysis for primary (in Section 4.4.3) and key secondary analyses (in Section 4.4.1.3) of continuous endpoints to	To comply with FDA's advice.

SAP Version	Approval Date	Change	Rationale		
version		account for potential unequal residual variances			
		with different group sizes.			
		Added treatment regimen analysis for the	To implement FDA's advice.		
		selected secondary and tertiary endpoints (fasting			
		serum glucose, fasting glucose from SMBG, and			
		selected CGM parameters in Sections 4.1 and			
		4.4.2.1.			
		Added missing data at baseline will be imputed	Addition.		
		using MI approach under MAR assumption in			
		Section 4.4.1.			
		Added adjustment for covariates and added	To implement FDA's advice.		
		appropriate baseline covariates for the binary			
		targets in Section 4.5.1.2. Also suggested a			
		missing data imputation for missing			
		hypoglycemia incidence.			
		Added sensitivity analysis that considers all	To implement FDA's feedback		
		hypoglycemic events as one hypoglycemic event	for SAP of the trial I8H-MC-		
		until a succeeding glucose value is \geq 70 mg/dL in	BDCV.		
		Section 4.6.3.1.1.1.			
		Added Section 4.6.4 analysis for device product	According to the new SAP		
		complaints.	template requirement		
		Updated the subgroups for race in Section 4.7.2.	To implement FDA's advice.		
		Clarified definitions of valid CGM period and	To implement FDA's advice.		
		visit; Added sensitivity analysis for selected			
		CGM parameters that derived from all data in			

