4.5.1.2. Binary outcomes for HbA1c target

For analysis of the binary outcomes, the details are provided in the table below:

Analysis Population	All participants in EAS1 with non-missing baseline measure		
Analysis	All non-missing observations at baseline and at the specified timepoints regardless of the use of		
Data	study intervention or rescue medications.		
Endpoint	1) HbA1c target (< 7% or \leq 6.5%) at the specified timepoints;		
	2) The composite of		
	a) binary outcome of HbA1c <7% at Week 26, and,		
	b) binary outcome of no nocturnal level 2 or 3 hypoglycemia during treatment phase up to		
	Week 26.		
	3) The composite of		
	a) binary outcome of HbA1c <7% at Week 26, and,		
	b) binary outcome of no level 2 or 3 hypoglycemia during treatment phase up to Week 26		
	with "Yes" indicating achieving the target (in respective endpoints defined above).		
Missing	1) For HbA1c, missing values at the specified timepoints will be imputed using the same		
Data	method for the primary endpoint (Section 4.3.2).		
	2) For hypoglycemia that are included in the composite endpoints, a participant who		
	discontinued both treatment and treatment period before Week 26 (Visit 22) is considered as		
	a non-responder (i.e. experienced the event).		
Analysis	These endpoints will be analyzed using a logistic regression model including		
Model	- independent variables of treatment,		
	- strata (country, and the type of basal insulin at randomization),		
	- baseline HbA1c value		
	- additionally, for the composite endpoint		
	 baseline incidence of hypoglycemia and, 		
	• interaction term of baseline HbA1c value * baseline incidence of		
	hypoglycemia; if the model fails to converge, the interaction term will be		
	removed.		
	The unconditional treatment group effect will be assessed based on a robust variance estimator		
	for g-computation estimators (Ye et al. 2023). The estimated treatment group-specific odds ratio,		
	p-value, and 95% CI will be used for treatment comparison. The statistical inference will be		
	based on the multiple imputation framework by Rubin (1987).		

Abbreviations: EAS1 = efficacy analysis set 1; HbA1c = hemoglobin A1c.

Note 1: Levels of hypoglycemia events and nocturnal events are defined in Section 4.6.3.1.1.

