4.9. Changes to Protocol-Planned Analyses

There are no changes to the analyses described in the protocol but additional details are provided.

5. Sample Size Determination

Approximately 939 participants will be randomly assigned to LY3209590 and insulin degludec in a 2:1 ratio. With the assumption of 15% dropout at Week 26 (Visit 22), approximately 532 and 266 participants will complete 26 weeks of treatment on LY3209590 and insulin degludec, respectively.

The primary objective of this study is to test the hypothesis that LY3209590 is noninferior to insulin degludec on glycemic control as measured by change from baseline to Week 26 (Visit 22) in HbA1c in participants with T2D currently on basal insulin.

Assuming a NIM of 0.4%, no true difference between treatment groups, and a SD of 1.1%, 798 completers (532 on LY3209590 and 266 on insulin degludec) will provide greater than 99% statistical power to show noninferiority between LY3209590 and insulin degludec using the upper limit of a 2-sided 95% confidence interval (LY3209590 – insulin degludec). This sample size also has at least 95% statistical power to show noninferiority between LY3209590 and insulin degludec) and insulin degludec using a 0.3% NIM at Week 26 (Visit 22).

The 798 completers will provide 95% statistical power to demonstrate the superiority (LY3209590 vs. insulin degludec) of change in HbA1c from baseline to 26 weeks (assuming a SD of 1.1% and true mean difference is -0.3%) using the alpha of 0.05.

The 798 completers will provide at least 95% statistical power to show the superiority of the percentage of time in glucose range between 70 and 180 mg/dL (3.9 and 10.0 mmol/L) inclusive during the CGM session prior to Week 26 (Visit 22) between LY3209590 and insulin degludec (assuming a SD of 18% and true mean difference is 5%) at alpha = 0.05.

The 798 participants will provide at least 80% statistical power to show the superiority of the event rate of clinically significant nocturnal hypoglycemia (<54 mg/dL [3.0 mmol/L] or severe) during treatment phase up to Week 78 (assuming event rate of 0.67 [SD = 2.6] and 1.1 [SD = 2.6] events per participant per year for LY3209590 and insulin degludec, respectively) using a negative binomial distribution at alpha = 0.05.

6. Supporting Documentation

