6.6. Appendix 6: Derivation of CGM Variables

Blinded CGM will be worn by participants at the following designated weeks:

- Two weeks in screening/lead-in period with the data download at Week 0 (Visit 3),
- Four weeks after the initiation of study treatment with the data download at Week 4 (Visit 7),
- Four weeks near the end of weekly titration period with the data download at Week 12 (Visit 15),
- Four weeks near the primary endpoint with the data download at Week 26 (Visit 22),
- Four weeks near the end of 1-year treatment with the data download at Week 52 (Visit 30),
- Four weeks near the end of study treatment period with the data download at Week 78 (Visit 37), and
- Four weeks after the end of study treatment period with the data download at Week 83 (Visit 802).

Linear interpolation will be used to impute the missing glucose readings during intervals >7 minutes and ≤ 15 minutes. Missing data will be imputed at a 5-minute interval using the BG value before and the one after the interval.

For example, the BG reading before the interval is 50 mg/dL at time 100 min, and the BG reading after interval is 70 at time 115 min, then the missing records will be imputed as:

- at time 105 min, BG reading=50+5*(70-50)/(115-100)=56.7, and
- at time 110 min, BG reading=50+10*(70-50)/(115-100)=63.3.

Glucose reading intervals >15 minutes will be treated as missing data and not be counted in the length of the analysis periods.

As shown in the table below, all the CGM derivations are based on the data from valid CGM periods of a day and period unless otherwise specified.

Period	Definition	Minimum Valid CGM Time Period for a Session		
Valid CGM Day	\geq 70% of expected values	\geq 3 valid CGM days within a visit defines a valid		
(00:00-23:59)	available (≥202 of 288 values)	CGM visit. A valid CGM session only includes valid		
		CGM visits.		
Valid CGM Nighttime	\geq 70% of expected values	\geq 3 valid CGM Nighttime periods within a visit		
(00:00-05:59)	available (≥50 of 72 values)	defines a valid CGM visit. A valid CGM session for		
		nighttime only includes valid CGM visits.		
Valid CGM Daytime	\geq 70% of expected values	\geq 3 valid CGM Daytime periods within a visit defines		
(06:00-23:59)	available 151 of 216 values)	a valid CGM visit. A valid CGM session for daytime		
		only includes valid CGM visits.		

Abbreviation: CGM = continuous glucose monitoring.

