The duration (in minutes) within the glucose range will then be calculated as the average percentage of time within the glucose range times the length of the period (24-hour, 18-hour, and 6-hour, for the periods of 24 hour, daytime or nighttime, respectively).

According to the guidance (Battelino et al. 2019), the following CGM targets of glycemic control will also be derived during a 24-hour period.

• The percentage of time within a normal glycemia range (defined as between 70 mg/dL and 180 mg/dL [3.9 and 10.0 mmol/L] inclusive) >70%.

- The percentage of time within a hypoglycemia range (defined as <70 mg/dL [3.9 mmol/L]) <4%.
- The percentage of time within a hypoglycemia range (defined as <54 mg/dL [3.0 mmol/L]) <1%.
- The percentage of time within a hyperglycemic range (defined as >180 mg/dL [10.0 mmol/L]) <25%.
- The percentage of time within a hyperglycemic range (defined as >250 mg/dL [13.9 mmol/L]) <5%.

In addition, according to the guidance in 2023 (Battelino et al. 2023), 2 composite endpoints will be derived during a 24-hour period:

- >70% time in range 70 -180 mg/dL (3.9 10.0 mmol/L inclusive) and <4% time below range <70 mg/dL (<3.9 mmol/L); and
- >70% time in range 70 -180 mg/dL (3.9 10.0 mmol/L inclusive) and <1% time below range <54 mg/dL (<3.0 mmol/L).

The daily duration (in minutes) of time within a glucose range (defined as <54 mg/dL [3.0 mmol/L]; <70 mg/dL [3.9 mmol/L] and \geq 54 mg/dL [3.0 mmol/L]; <0 mg/dL [3.9 mmol/L]; \geq 70 mg/dL[3.9 mmol/L] and \leq 140 mg/dL [7.8 mmol/L]; \geq 70 mg/dL [3.9 mmol/L] and \leq 180 mg/dL [10.0 mmol/L]; >180 mg/dL[10.0 mmol/L] and \leq 250 mg/dL[13.9 mmol/L]; >250 mg/dL [13.9 mmol/L]) will be merged with the dose administration data to get the summary of daily time in each glucose range since dose administration in the each CGM session in the treatment period. For LY3209590, days relative to dose administration will be derived as 0 (dosing day), and then 1, 2, ..., up to 6 days after most recent dose administration but before the next dose administration. The average daily time in hypoglycemia for the given day (0 to 6) relative to the dose administration among valid CGM days (with at least 70% data per day) during each CGM session will be used in the analysis.

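### The models for the yes/no CGM targets adjust, read literally, for baseline target status; the continuous baseline percentage would give modestly more power for time in range >70%

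*SAP*

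**What the plan says.** SAP 4.4.2.1.1 gives the model for the CGM targets as "Longitudinal logistic regression model with independent variables of treatment, strata" (country, type of basal insulin, baseline HbA1c stratum), then visit, treatment by visit, and a last term: "baseline of the dependent variable will be used to analyze CGM targets of glycemic controls".

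SAP 6.6.1 introduces the targets with "the following CGM targets of glycemic control will also be derived during a 24-hour period". There are five cut-offs on percentages of time: 70-180 mg/dL above 70%, <70 mg/dL below 4%, <54 mg/dL below 1%, >180 mg/dL below 25% and >250 mg/dL below 5%. Two composites pair the first with one of the two hypoglycemia cut-offs. Each outcome is met or not met.

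The underlying baseline percentages are available. SAP 6.6 schedules a two-week blinded session in the lead-in, SAP 4.1 takes the baseline of CGM parameters from the session before first dose, and SAP 6.6.1 derives the percentages for each session.

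For the HbA1c <7% and ≤6.5% targets, SAP 4.5.1.2 lists "baseline HbA1c value" as a covariate, which is the measured value and not the target status. The SAP version history records that Version 4 added "appropriate baseline covariates for the binary" targets, for Section 4.5.1.2 only.

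**The concern.** The dependent variable is a threshold on a continuous percentage, so its literal baseline is the same threshold applied at baseline. That discards how far each participant stood from the cut-off, which is information about the chance of meeting the target later. A programmer following the text would code the yes/no version. What is at stake is some power for the treatment comparison on target attainment, lost although the better covariate is already in the dataset. The HbA1c targets are the closest analogue in the plan, being cut-offs on a continuous measure, and they are handled the other way.

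**Working it through.** **1. The plan's own figure.** The sample size section gives no power for the binary CGM targets. The nearest figure is at least 95% for continuous time in range. Inputs: 626 and 313 randomized, "With the assumption of 15% dropout at Week 26", SD 18, difference 5, two-sided alpha 0.05.

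- Completers: 626 × 0.85 = 532.1 and 313 × 0.85 = 266.05.
- SE = 18 × √(1/532 + 1/266) = 1.352.
- Power ≈ Φ(5/1.352 − 1.96) = Φ(1.74) = 95.9%.

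The figure reproduces.

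**2. Set-up for the >70% target.** Simulated trials had 532 and 266 participants, with baseline and Week 26 time in range bivariate normal, SD 18, and a treatment difference of 5 points. Logistic regression used treatment, HbA1c stratum, and either baseline status (>70% yes/no) or the continuous baseline. There were 2,000 trials per scenario, and both models were fitted to the same data.

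Assumptions not in the documents: correlation between baseline and Week 26, mean baseline time in range, a 5-point rise under degludec, an HbA1c to time-in-range correlation of −0.5, and normality. One visit is modeled, and country and basal insulin type are omitted.

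**3. Results.** The variance ratio is that of the marginal risk difference (standardized over covariates), status model over continuous model.

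| Correlation | Mean baseline | Power, status | Power, continuous | Gain (points) | Variance ratio |
|---|---|---|---|---|---|
| 0.3 | 50 | 76.8% | 78.2% | 1.4 | 1.022 |
| 0.3 | 60 | 84.9% | 85.8% | 0.9 | 1.021 |
| 0.3 | 65 | 84.4% | 85.5% | 1.1 | 1.020 |
| 0.5 | 50 | 79.0% | 81.4% | 2.4 | 1.063 |
| 0.5 | 60 | 86.7% | 88.0% | 1.3 | 1.065 |
| 0.5 | 65 | 87.0% | 89.1% | 2.1 | 1.060 |
| 0.7 | 50 | 85.0% | 90.1% | 5.1 | 1.142 |
| 0.7 | 60 | 92.1% | 95.2% | 3.1 | 1.145 |
| 0.7 | 65 | 92.2% | 94.8% | 2.6 | 1.137 |

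The loss in participants is 798 × (1 − 1/ratio). For a ratio of 1.065 this is 798 × 0.061 = 49. Across the table it is 16-17, 45-49 and 96-101 at correlations 0.3, 0.5 and 0.7. Keeping the HbA1c stratum in the model does not recover the loss.

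**4. Where the gain shows.** In a rerun, the standard error of the conditional log odds ratio rose with the continuous baseline, from 0.162 to 0.168 at correlation 0.5 and from 0.175 to 0.188 at 0.7. The test statistic improves because the conditional estimate grows by more.

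**5. A skewed target.** Time <54 mg/dL was simulated as lognormal (log-SD 1.5, 75-95% of participants meeting the <1% target, 532/266; all but the group sizes assumed). Replacing status by the raw baseline percentage gave squared-z ratios of 0.99-1.00 at correlation 0.3, 1.00-1.01 at 0.5 and 1.03-1.06 at 0.7, with power changing by −1.3 to +1.0 points. A second set of lognormal runs gave ratios of 0.99-1.05 and power changes of −1.7 to +1.9 points, with only a small gain from a log transform.

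The status model failed to fit in 26 of 1,500 trials in the most extreme setting (95% meeting the target, correlation 0.3), in 1 of 1,500 in another, and never in the other seven. In the second set it failed in 6 of 1,000 trials in one extreme setting.

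**The case against.** Three objections carry weight.

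First, the wording matches the MMRM description in SAP 4.3.2 and may have been carried over. The sponsor may already mean the continuous percentage, since SAP 4.1 defines a baseline for CGM parameters. This stands as a possibility. If it is the intent, the text still needs to say so, because the dependent variable of a logistic model is the yes/no outcome.

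Second, a reader might infer that the rest of the SAP uses continuous baselines for binary outcomes and that this model alone departs from them. The documents do not support that. The incidence models in SAP 4.6.3.1.1 for Level 1, Level 2 and Level 2/3 events, and those in SAP 4.6.3.1.2, adjust for baseline incidence. The composite HbA1c targets in SAP 4.5.1.2 also add a yes/no hypoglycemia term. The HbA1c targets are the closest analogue, not evidence of a uniform rule.

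Third, a reader might infer a gain across all seven targets, or convergence trouble where nearly everyone meets a target at baseline. Neither is supported. For time <54 mg/dL the raw percentage brought essentially nothing, and fitting failures were rare. The documents give no baseline attainment rates from which to argue otherwise.

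**Conclusion.** The point holds in a limited form. As written, SAP 4.4.2.1.1 specifies a dichotomized baseline where a continuous one is already derived. For time in range >70% this costs about 1 to 5 points of power at assumed correlations of 0.3 to 0.7. The direction was the same in all nine scenarios; the size rests on the assumed correlation and mean time in range and on a one-visit simplification. The >180 mg/dL target was not simulated.

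It would be wrong to describe the gain as a tighter conditional odds ratio. It appears in power and, if a marginal effect is reported, in that effect's precision. SAP 4.4.2.1.1 does not call for a marginal estimate, unlike SAP 4.5.1.2.

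The impact is small. Attainment of CGM targets is not in the endpoint table of SAP 1.1 and lies outside the multiplicity procedure of SAP 2.1. The key secondary time-in-range analysis already adjusts for its continuous baseline.

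**What to change.** In SAP 4.4.2.1.1, replace the generic baseline term with named covariates:

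- **Time in range >70%:** continuous baseline percentage of time in 70-180 mg/dL.
- **Time >180 mg/dL below 25%:** continuous baseline percentage of time >180 mg/dL, by the same reasoning.
- **Two composites:** include the continuous baseline time in range.
- **Targets for <70, <54 and >250 mg/dL:** a log-type transform of the baseline percentage, or keep baseline status. State which.

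The cost is a few lines of SAP text and a small programming change. It needs no new data and no design change, and should be settled before unblinding.
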